Appendix G CYTOCHROME P450 3A4 (CYP3A4) SUBSTRATES WITH NARROW THERAPEUTIC RANGE

CYP3A4 substrates with narrow therapeutic range refers to drugs whose exposure-response indicates that increases in their exposure levels by the concomitant use of CYP3A4 inhibitors may lead to serious concerns. Investigators should seriously consider switching to an alternative agent whenever possible, or exercise caution and be alert for signs requiring dose modification. The following list provides examples of CYP3A4 substrates with narrow therapeutic range (note that this is not an exhaustive list):

Alfentanil	Diergotamine	Quinidine
Astemizolea	Ergotamine	Sirolimus
Cisapridea Cyclosporine	Fentanyl Pimozide	Tacrolimus Terfenadine ^a
^a Not available in the United States.		

Appendix H RESPONSE CRITERIA FOR MULTIPLE MYELOMA
Summary of International Myeloma Working Group Uniform Response Criteria
(IMWG-URC)

Response Subcategory^a	Response Criteria
sCR ^b	
 • Negative immunofixation on the serum and urine and • Disappearance of any soft tissue plasmacytomas and • < 5% plasma cells in bone marrow and • Normal SFLC ratio and • Absence of clonal cells in bone marrow^c
CR ^b	
 • Negative immunofixation on the serum and urine and • Disappearance of any soft tissue plasmacytomas and • < 5% plasma cells in bone marrow
VGPR ^{b, d}	
 • Serum and urine M-protein detectable by immunofixation, but not on electrophoresis or • $\geq 90\%$ reduction in serum M-component with urine M-component < 100 mg per 24 hours
PR ^{b, d}	
 • $\geq 50\%$ reduction of serum M-protein and reduction in 24-hour urinary M-protein by $\geq 90\%$ or to < 200 mg per 24 hours • If the serum and urine M-protein are not measurable, a decrease $\geq 50\%$ in the difference between involved and uninvolved FLC levels is required in place of the M-protein criteria. • If the serum and urine M-protein are not measurable, a decrease $\geq 50\%$ in the difference between involved and uninvolved FLC levels is required in place of the M-protein criteria. • If present at baseline, a $\geq 50\%$ reduction in the size of soft tissue plasmacytomas is also required^{d, e}
Stable disease	
 • Not meeting criteria for CR, VGPR, PR, or PD

Footnoted defined on next page

Summary of International Myeloma Working Group Uniform Response Criteria (IMWG-URC) (cont'd)

Response Subcategory ^a	Response Criteria
PD ^c	
Any one or more of the following increase of $\geq 25\%$ from lowest response value in:
 
 • Serum M-component (absolute increase must be ≥ 0.5 g/dL) and/or • Urine M-component (absolute increase must be ≥ 200 mg per 24 hours) and/or • Only in subjects without measurable serum and urine M-protein levels: the difference between involved and uninvolved FLC levels (absolute increase must be > 10 mg/dL) • Only in subjects without measurable serum and urine M-protein levels and without measurable disease by FLC levels, bone marrow PC percentage (absolute percentage must be $\geq 10\%$) • Bone marrow plasma cell percentages (absolute % must be $\geq 10\%$) 
Definite development of new bone lesions or soft tissue plasmacytomas or definite increase in size of existing bone lesions or soft tissue plasmacytomas^{f, g, h}
 
Development of hypercalcemia (corrected serum calcium > 11.5 mg/dL or 2.65 mmol/L) attributed solely to the plasma cell proliferative disorder

Page 2 of 2

Sources: [Durie 2006](#); [Rajkumar 2011](#).

CR = complete response; sCR = stringent complete response; FLC = serum free light chain; PD = progressive disease; PR = partial response; SFLC = serum free light chain; VGPR = very good partial response.

^a Subjects with measurable disease in both serum (SPEP) and urine (UPEP) at study entry are required to meet response criteria in both UPEP and SPEP in order to qualify for a PR or better. Conversely, it should be noted that criteria for PD only need to be met and confirmed in 1 parameter.

^b **All response categories (CR, sCR, VGPR, PR) require 2 consecutive assessments** made at any time before the institution of any new therapy, as well as no known evidence of progressive or new bone lesions if radiographic studies were performed. Radiographic studies are not required to satisfy these response requirements. Bone marrow assessments are not required to be confirmed by repeat testing, but these should be done within 30 days of the confirmatory assessment if appropriate for the response category.

^c Presence/absence of clonal cells is based upon the κ/λ ratio. An abnormal κ/λ ratio by immunohistochemistry and/or immunofluorescence requires a minimum of 100 plasma cells for analysis. An abnormal ratio reflecting presence of an abnormal clone is κ/λ of $> 4:1$ or $< 1:2$.

^d Response criteria for all categories and subcategories of response except CR and VGPR are applicable only to subjects that have “measurable” disease defined by at least one of SPEP ≥ 1.0 g/dL or UPEP ≥ 200 mg per 24 hours; except for assessment of sCR, CR, or VGPR, subjects with measurable disease restricted to SPEP will need to be followed only by SPEP. Correspondingly, subjects with measurable disease restricted to UPEP will need to be followed only by UPEP.

^e **Determination of PD based on M-protein, hypercalcemia, or FLC while on study requires 2 consecutive assessments** made at any time before classification of PD and/or the institution of new therapy. Serum M-component increases of ≥ 1 g/dL are sufficient to define progression if starting M-component is ≥ 5 g/dL.

^f Plasmacytomas: A definite increase in the size is defined as a $\geq 50\%$ increase as measured serially by the sum of the products of the cross-diameters of the measurable lesion. A plasmacytoma is considered measurable if the longest diameter is at least 1 cm and the product of the cross diameters is at least 1 cm^2 . Plasmacytomas of lesser size will be considered nonmeasurable.

^g The requirement for bi-directional measurements will only be applied to plasmacytomas.

^h The plasmacytoma specifications for PD are based on the sponsor’s interpretation of the IMWG-URC and practical considerations for study execution.

Definition of Minimal Response and Near-Complete Response per EBMT Criteria

Response Subcategory	Response Criteria
MR ^a	≥ 25 but < 49% reduction in serum M-protein and a 50-89% reduction in 24-hour urinary M-protein, which still exceeds 200 mg per 24 h
	For subjects with non-secretory myeloma only, 25-49% reduction in plasma cells in a bone marrow aspirate and on trephine biopsy, if biopsy is performed.
	25-49% reduction in the size of soft tissue plasmacytomas (by radiography or clinical examination)
	No increase in size or number of lytic bone lesions (development of compression fracture does not exclude response)
nCR ^a	Immunofixation-positive response. Absence of M-protein on electrophoresis, independent of the immunofixation test status, stable bone disease, and a normal serum calcium concentration,

Sources: [Bladé 1998](#), [Kyle 2009](#), [Richardson 2003](#).

EBMT = European Group for Blood and Marrow Transplantation; MR = minimal response; nCR = near- complete response.

^a **Response categories (MR and nCR) require 2 consecutive assessments** made at any time before the institution of any new therapy, as well as no known evidence of progressive or new bone lesions if radiographic studies were performed. Radiographic studies are not required to satisfy these response requirements. Bone marrow assessments are not required to be confirmed by repeat testing.

**Appendix I BLOOD SAMPLES FOR PHARMACOKINETIC AND PHARMACODYNAMIC/PROTEOMIC ANALYSES:
SAMPLING TIMES**

Phase 1b Sampling Time Points (continuous dosing subjects only)

Time Point									
Cycle	Day	Predose	15 min Postdose	30 min Postdose	1 hour Postdose	2 hours Postdose	4 hours Postdose	6 hours Postdose	8 hours Postdose
Schedule: 5 Consecutive Days Bimonthly (Days 1–5 of Each 14-day Treatment Cycle)									
1	1	PK PDn	PK	PK	PK	PK	PK PDn	PK	PK PDn
1	2	PK PDn	—	—	—	—	—	—	—
2	1	PK PDn	PK	PK	PK	PK	PK PDn	PK	PK PDn
Schedule: 2 Consecutive Days Weekly (Days 1, 2, 8, and 9 of Each 14-day Treatment Cycle)									
1	1	PK PDn	PK	PK	PK	PK	PK PDn	PK	PK PDn
1	2	PK PDn	—	—	—	—	—	—	—
2	1	PK PDn	PK	PK	PK	PK	PK PDn	PK	PK PDn

PK = blood draw for pharmacokinetic analysis; PDn = blood draw for pharmacodynamic analyses; — indicates that no blood sample is obtained.

Note: Oprozomib must be taken in the fasted state (at least 2 hours after a meal and fasting for at least 2 hours after dosing) on days in which PK sampling is taken after a dose. On all other days including non-PK days and days in which only a predose PK sample is taken, it is recommended that oprozomib is administered with food (i.e., within approximately 30 minutes after eating). Subjects switching from Oprozomib Tablet to Oprozomib ER Tablet should follow Day 1 PK sampling as described for step-up dosing (predose to 7 hours postdose) on Day 1 of the cycle prior and Day 1 of the cycle subsequent to the switch.

Phase 1b Sampling Time Points (step-up dosing subjects only)

Time Point									
Cycle	Day	Predose	15 min Postdose	30 min Postdose	1 hour Postdose	2 hours Postdose	4 hours Postdose	6 hours Postdose	7 hours Postdose
Schedule: 5 Consecutive Days Bimonthly (Days 1–5 of Each 14-day Treatment Cycle)									
1	1	PK PDn	PK	PK	PK	PK	PK PDn	PK PDn	PK
1	2	PK PDn	—	—	—	—	—	—	—
2	1	PK PDn	PK	PK	PK	PK	PK PDn	PK PDn	PK
2	2	PK PDn	—	—	—	—	—	—	—
Schedule: 2 Consecutive Days Weekly (Days 1, 2, 8, and 9 of Each 14-day Treatment Cycle)									
1	1	PK PDn	PK	PK	PK	PK	PK PDn	PK PDn	PK
1	2	PK PDn	—	—	—	—	—	—	—
2	1	PK PDn	PK	PK	PK	PK	PK PDn	PK PDn	PK
2	2	PK PDn	—	—	—	—	—	—	—

PK = blood draw for pharmacokinetic analysis; PDn = blood draw for pharmacodynamic analyses; — indicates that no blood sample is obtained.

Note: Oprozomib must be taken in the fasted state (at least 2 hours after a meal and fasting for at least 2 hours after dosing) on days in which PK sampling is taken after a dose. On all other days including non-PK days and days in which only a predose PK sample is taken, it is recommended that oprozomib is administered with food (i.e., within approximately 30 minutes after eating).

Phase 2 Sampling Time Points

Time Point									
Cycle	Day	Predose	15 min Postdose	30 min Postdose	1 hour Postdose	2 hours Postdose	4 hours Postdose	6 hours Postdose	7 hours Postdose
Schedule: 5 Consecutive Days Bimonthly (Days 1–5 of Each 14-day Treatment Cycle)									
1	1	PK PDn/P	PK	PK	PK	PK	PK PDn/P	PK PDn/P	PK
1	2	PK PDn/P	—	—	—	—	—	—	—
2	1	PK PDn/P	PK	PK	PK	PK	PK PDn/P	PK PDn/P	PK
2	2	PK PDn/P	—	—	—	—	—	—	—
Schedule: 2 Consecutive Days Weekly (Days 1, 2, 8, and 9 of Each 14-day Treatment Cycle)									
1	1	PK PDn/P	PK	PK	PK	PK	PK PDn/P	PK PDn/P	PK
1	2	PK PDn/P	—	—	—	—	—	—	—
2	1	PK PDn/P	PK	PK	PK	PK	PK PDn/P	PK PDn/P	PK
2	2	PK PDn/P	—	—	—	—	—	—	—

PK = blood draw for pharmacokinetic analysis; PDn/P = blood draw for pharmacodynamic and proteomic analyses; — indicates that no blood sample is obtained.

Note: Oprozomib must be taken in the fasted state (at least 2 hours after a meal and fasting for at least 2 hours after dosing) on days in which PK sampling is taken after a dose. On all other days including non-PK days and days in which only a predose PK sample is taken, it is recommended that oprozomib is administered with food (i.e., within approximately 30 minutes after eating).

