3.2 NUMBER OF CENTERS

Approximately 12 sites in the US and 4 sites in France will be recruited for participation in the protocol. Sites that do not enroll subjects within 6 months of site initiation may be terminated.

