7.6 DISEASE RESPONSE ASSESSMENTS

The schedules of disease assessments for subjects treated on either treatment schedule are provided in [Appendix E](#). Beginning with Cycle 3, assessments are to be completed every 4 weeks for the first year while on study drug and then changed to every 8 weeks (4 cycles) after Cycle 26. Subjects enrolled in the Phase 2 portion of the study will be evaluated for disease response following the IMWG-URC; evaluations will also include MR and nCR from EBMT criteria ([Appendix F](#)).

Disease response will be assessed by the investigator.

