7.5.2 Progression Free Survival

Progression free survival (PFS) is defined as number of months (one month = 30.4 days) between start of treatment and first evidence of documented disease progression or death (due to any cause), whichever occurs first. Disease progression will be determined using IMWG-URC and will be determined by the investigator.

$$PFS = \text{Earliest date of disease progression, death, or censoring} - \text{Date of first dose} + 1 \text{ and expressed in months}$$

The duration of PFS will be right-censored for subjects who meet 1 of the following conditions: 1) starting a new anticancer therapy before documentation of disease progression or death; 2) death or disease progression immediately after more than 1 consecutively missed disease assessment visit or; 3) alive without documentation of

disease progression before the data cutoff date. For such subjects, the analysis of PFS will be right-censored according to the conventions described in Table 1.

Table 1: Date of Progression or Censoring for PFS and DOR

Situation	Date of Progression or Censoring	Outcome
No baseline disease assessments	Date of first dose	Censored
New anticancer therapy started before documentation of PD or death	Date of last disease assessment prior to start of new anticancer therapy	Censored
Death or PD immediately after more than 1 consecutively missed disease assessment visit	Date of last disease assessment visit without documentation of PD that is before the first missed visit	Censored
Alive and without PD documentation	Date of last disease assessment	Censored
Death or PD between planned disease assessments	Date of death or first disease assessment showing PD, whichever occurs first	Progressed
Death before first disease assessment	Date of death	Progressed

PD = progressive disease

Kaplan-Meier method will be used to estimate the distribution of PFS and the median and other quartiles in addition to the corresponding two-sided 95% confidence intervals.

Duration of follow-up for PFS will be summarized according to the Kaplan-Meier estimate of potential follow-up also termed “reverse Kaplan-Meier” (Schemper 1996).

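### Appendix H gives the hypercalcemia limit for progression as 11.5 mg/dL or 2.65 mmol/L; these are different calcium levels, and nothing says which governs

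*Protocol*

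**What the plan says.** The PD row of the IMWG-URC table in Protocol Appendix H gives hypercalcemia as a route to progression: "Development of hypercalcemia (corrected serum calcium > 11.5 mg/dL or 2.65 mmol/L) attributed solely to the plasma cell proliferative disorder". Two footnotes to that table set its weight:

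- Calcium alone can establish PD, because "criteria for PD only need to be met and confirmed in 1 parameter".
- The finding has to be repeated: "Determination of PD based on M-protein, hypercalcemia, or FLC while on study requires 2 consecutive assessments".

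The judgement is made locally. Protocol Section 7.6 states: "Disease response will be assessed by the investigator". SAP Section 7.5.2 repeats this for PFS: "Disease progression will be determined using IMWG-URC and will be determined by the investigator". SAP Section 7.5 uses the investigator's progression call for PFS, TTP and DOR, and Section 7.5.5 takes its progression dates for duration of clinical benefit from the PFS rules. Protocol Sections 3.1 and 6.1 make progression one of the reasons for ending treatment.

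No other part of either document gives a calcium limit for PD, a conversion factor, or a rule on which unit prevails. SAP Section 7.6.2 grades calcium for toxicity only.

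**The concern.** The criterion joins a mass concentration and a molar concentration as if they were one limit in two units. If they differ, there are two PD definitions in one line, and the investigator's choice between them is unguided. The choice could follow the unit on the laboratory report, or it could be whichever figure the investigator reads first.

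PD is the event in three secondary time-to-event endpoints and in the SAP's added duration of clinical benefit. It also ends treatment. A subject in the gap could be recorded as progressed, or as continuing, for a reason unrelated to the disease.

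**Working it through.** **Inputs**

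- From Appendix H: 11.5 mg/dL and 2.65 mmol/L.
- Molar mass of calcium: 40.078 g/mol. This is a physical constant that the documents do not give. Rounded values of 40.0 and 40.08 are tried as well.

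**Formula.** mmol/L = (mg/dL × 10) / molar mass; in reverse, mg/dL = mmol/L × molar mass / 10.

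**Trying to reproduce the stated pair**

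- 11.5 × 10 / 40.078 = 2.869 mmol/L, against 2.65 stated.
- 2.65 × 40.078 / 10 = 10.62 mg/dL, against 11.5 stated.

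The pair does not reproduce.

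| Molar mass used | 11.5 mg/dL in mmol/L | 2.65 mmol/L in mg/dL | Gap in mg/dL |
|---|---|---|---|
| 40.0 | 2.875 | 10.60 | 0.90 |
| 40.078 | 2.869 | 10.62 | 0.88 |
| 40.08 | 2.869 | 10.62 | 0.88 |

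**Size of the gap**

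- 2.869 − 2.65 = 0.22 mmol/L.
- 11.5 − 10.62 = 0.88 mg/dL.
- 0.88 / 11.5 = 7.6%, with the molar figure the lower of the two.

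**Could rounding or another unit explain it?**

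- Anything that rounds to 11.5 mg/dL (11.45 to 11.55) converts to 2.857 to 2.882 mmol/L.
- Anything that rounds to 2.65 mmol/L (2.645 to 2.655) converts to 10.60 to 10.64 mg/dL.
- Read as milliequivalents, 11.5 mg/dL is 2 × 2.869 = 5.74 mEq/L.
- For the two figures to agree, calcium would need a molar mass of 115 / 2.65 = 43.4.

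None of these closes the gap.

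**A worked case.** Take a confirmed corrected calcium of 11.0 mg/dL, which is 11.0 × 10 / 40.078 = 2.74 mmol/L. It is above 2.65 mmol/L, so PD is met on that figure. It is below 11.5 mg/dL, so PD is not met on the other.

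**Who is affected.** All of these must hold for the gap to decide an outcome:

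1. The hypercalcemia is new.
2. Corrected calcium is above 10.6 and up to 11.5 mg/dL.
3. It is confirmed at a second consecutive assessment.
4. It is ascribed to the myeloma alone.
5. No other PD criterion has been met by that date.

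**The primary test.** Protocol Section 10.2 and SAP Section 2.3 reject at 12 or more responders of 46, against a 15% null, with power at 30%. That rule has exact one-sided alpha 0.035 and power 0.767, which matches the stated 77%. The calcium limit does not enter it.

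**The case against.** The strongest case against the point accepts the conversion and disputes the consequence.

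- **Site units are not documented.** A reader might infer that French sites use the lower limit and US sites the higher, since "Approximately 12 sites in the US and 4 sites in France will be recruited". The documents do not support that: they give countries, not calcium units. The cut-offs for M-protein, light chains, creatinine and glucose are all in mass units, so mg/dL may have been the working unit everywhere. A country difference is therefore only a possibility.
- **Not everyone in the band is reclassified.** A reader might count every calcium value between the two limits. That goes too far: the criterion also requires new onset, confirmation and sole attribution, and the gap changes nothing if another PD parameter is already met.
- **The affected endpoints are descriptive.** PFS, TTP and DOR are summarised by Kaplan-Meier estimates with confidence intervals, without a hypothesis test or a country comparison. The only powered test concerns ORR.
- **It is late.** Protocol Section 1 and Appendix N say that the analysis and abbreviated report are complete. Under Amendment 4, chemistry for subjects still on treatment is done only when clinically indicated and at end of study.
- **The word joining the figures may mean that either suffices.** The lower figure would then govern and 11.5 mg/dL would be redundant. An investigator comparing a mg/dL result with 11.5 would still miss PD in the gap.
- **The pair may have been copied.** The table cites published criteria that cannot be checked here. Copying could explain the mismatch, but it would not make the figures equal.

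The first four limit the size of the problem and are accepted. None of the six reconciles the two figures or supplies a governing one.

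**Conclusion.** Wrong as written. The figures in "corrected serum calcium > 11.5 mg/dL or 2.65 mmol/L" differ by 0.22 mmol/L (0.88 mg/dL, about 8%), and neither document says which applies. This conclusion rests only on the molar mass of calcium and is secure.

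The consequence is narrow. For a subject who meets all five conditions in the working, PD depends on which figure is used. That can change the PD date behind PFS, TTP, DOR and duration of clinical benefit, and when treatment stops. The documents give no count of such subjects; the number is probably small, because PD resting on calcium alone inside a narrow band should be uncommon. The ORR decision rule and its power are not affected, and no country effect is shown.

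The documents cannot settle which figure was intended, and since PD ends treatment, this review does not choose between them.

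**What to change.** **Text.** The sponsor should reconcile the two figures so that Appendix H states one threshold with a correct conversion. This is a one-line correction once the intended value is settled.

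**Analysis.** Convert corrected calcium to one unit for all subjects, then check records above 10.6 and up to 11.5 mg/dL in both directions:

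1. PD that was called on hypercalcemia alone, which may be over-called if the higher figure was intended.
2. Confirmed values ascribed to the myeloma where PD was not called, which may be under-called if the lower figure was intended.

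A check limited to recorded PD would find only the first kind. Report any resulting change to PFS, TTP and DOR, and carry the same dates into duration of clinical benefit. As the abbreviated report is already complete, this would be a short supplement to it.

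**Cost.** Calcium and albumin are both in the full chemistry panel (Protocol Table 11), so no new data collection should be needed. Appendix H gives no formula for corrected calcium, so the check should name the one it uses. The second direction takes more work than the first, because it means screening calcium results in subjects without recorded PD and reviewing attribution for those in the band.

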4.1 INCLUSION CRITERIA

1. Diagnosis of multiple myeloma with measurable disease as indicated by 1 or more of the following:
 - a. Serum M-protein \geq 500 mg/dL
 - b. Urine M-protein \geq 200 mg/24 hour
 - c. Only for subjects without measurable serum and urine M-protein, serum free light chain: Involved free light chain (FLC) level \geq 10 mg/dL, provided serum FLC ratio is abnormal
2. Patients requiring therapy who have relapsed and/or are refractory to their last therapy and have been treated with at least 1, but not more than 5, lines of multiple myeloma

- therapy. Prior therapy must consist of at least 1 regimen that included lenalidomide and/or bortezomib. Patients should be considered to be appropriate candidates for a clinical study by their treating physicians. Relapsed patients must have previously achieved \geq MR on at least 1 line of therapy as assessed by the treating physician. Refractory patients are allowed, but it is not required that patients be refractory to their last therapy. Primary refractory patients are allowed in the Phase 1b portion of the study only.
3. Males and females \geq 18 years of age
 4. Eastern Cooperative Oncology Group Performance Status (ECOG PS) 0–2
 5. Adequate hepatic function, with bilirubin \leq 1.5 times the upper limit of normal (ULN) in the absence of Gilbert’s disease or hemolysis, aspartate aminotransferase (AST) \leq 3 times ULN, and alanine aminotransferase (ALT) \leq 3 times ULN
 6. Absolute neutrophil count (ANC) \geq 1000 cells/mcL, hemoglobin \geq 7.0 g/dL, and platelet count \geq 30,000 cells/mcL:
 - a. Patients must not have received platelet transfusions for at least 1 week prior to Screening.
 - b. Screening ANC must be independent of granulocyte colony-stimulating factor (G-CSF) and granulocyte-macrophage colony-stimulating factor (GM-CSF) support for at least 1 week and of pegylated G-CSF for \geq 2 weeks prior to first dose.
 - c. Patients may receive red blood cell (RBC) transfusions or receive supportive care with erythropoietin or darbepoetin in accordance with institutional guidelines.
 7. Calculated or measured creatinine clearance (CrCl) rate of \geq 30 mL/min calculated using the formula of Cockcroft and Gault $[(140 - \text{age}) \times \text{mass (kg)} / (72 \times \text{serum creatinine mg/dL})]$. Multiply result by 0.85 if female.
 8. Uric acid, if elevated, must be corrected to within laboratory normal range before dosing

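### Appendix H footnote d sets a higher serum threshold for scoring PR (1.0 g/dL) than inclusion criterion 1a sets for entry (0.5 g/dL), so some eligible subjects cannot be scored PR on M-protein but still count in the primary ORR

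*Protocol*

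**What the plan says.** **Entry.** Protocol 4.1, criterion 1, counts disease as measurable on any one of three grounds. The first is "Serum M-protein \geq 500 mg/dL". The second is urine M-protein of at least 200 mg/24 h. The third begins "Only for subjects without measurable serum and urine M-protein, serum free light chain: Involved free light chain (FLC) level" and requires an involved FLC of at least 10 mg/dL with an abnormal ratio.

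**Response.** Footnote d to the IMWG-URC table in Appendix H is marked on the VGPR and PR rows. It opens "Response criteria for all categories and subcategories of response except CR and VGPR are applicable only to subjects that have" measurable disease, and gives the meaning as "disease defined by at least one of SPEP ≥ 1.0 g/dL or UPEP ≥ 200 mg per 24 hours". It has no FLC route. The PR row has one: "If the serum and urine M-protein are not measurable", a fall of at least 50% "in the difference between involved and uninvolved FLC levels is required in place of the M-protein criteria". The row does not define when M-protein is not measurable.

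**Other uses of the term.** Footnote a ("Subjects with measurable disease in both serum (SPEP) and urine (UPEP) at study entry are required to meet response criteria in both" tests) and the PD row ("Only in subjects without measurable serum and urine M-protein levels: the difference between involved and uninvolved FLC levels") both depend on what is measurable, and neither gives a threshold.

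**Analysis.** PR or better is the Phase 2 primary endpoint. Protocol 10.2 and SAP 2.3 reject the null ORR of 15% with at least 12 responders of 46. Protocol 10.3.1 and SAP 4 and 7.5 base efficacy on all treated subjects. SAP 7.5.1 refers to IMWG-URC and EBMT and sets no measurability threshold.

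**The concern.** The urine thresholds agree and the serum thresholds differ twofold. A subject who enters on a serum M-protein of, say, 0.7 g/dL with little urinary protein has measurable disease for eligibility and not for PR. If that M-protein halves and nothing deeper follows, the literal rule gives no PR. The subject remains in the denominator and counts as a non-responder.

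Two consequences follow. If footnote d was applied, the primary ORR understates activity for these subjects. If it was set aside, their PRs rest on a threshold that the response appendix does not state. Response is assessed by the investigator (Protocol 7.6), so different sites could have resolved the conflict differently.

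**Working it through.** **Step 1: common units.** 500 mg/dL ÷ 1000 = 0.5 g/dL, against 1.0 g/dL in footnote d. Urine is 200 mg/24 h in both places.

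**Step 2: who falls between the definitions.**

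| Baseline disease | Criterion 1 | Footnote d | PR rule as written |
|---|---|---|---|
| Serum ≥ 1.0 g/dL | measurable | measurable | M-protein rule applies |
| Serum 0.5 to < 1.0, urine ≥ 200 | measurable | measurable by urine only | scorable, followed by urine |
| Serum 0.5 to < 1.0, urine < 200 | measurable | not measurable | M-protein rule closed; FLC rule uncertain |
| FLC only | measurable | not measurable | FLC rule in the PR row, contradicted by footnote d |

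The third row is the main problem. The FLC rule reaches these subjects only if not measurable in the PR row takes footnote d's meaning, which the text does not say. They also need not have an FLC level high enough to be informative. CR and VGPR are exempt from footnote d, and nCR is defined in the separate EBMT table, so those routes remain open to them.

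For the fourth row the fault is secondary, since an explicit PR rule exists. VGPR and nCR are not clean alternatives for that group. Neither has an FLC criterion, and absence of M-protein on electrophoresis may already hold at baseline.

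**Step 3: reach of the literal wording.** Footnote d exempts only CR and VGPR. Although its marker is not on the stable disease or PD rows, its words cover all categories, so SD and PD would be barred too. Treatment continuation needs SD (Protocol 3.1.1 and 6.3), and PFS and TTP need PD (Protocol 10.3.2; SAP 7.5.2 and 7.5.3).

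**Step 4: the plan's own figures.** Exact binomial, n = 46, reject at 12 or more:

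- P(X ≥ 12 | 46, 0.30) = 0.767, against the stated 77%.
- P(X ≥ 12 | 46, 0.15) = 0.035. A cut of 11 would give 0.074, so 12 is the right cut at 5%.

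**Step 5: illustration.** Let k of the 46 subjects be affected, with none of their responses counted and a true ORR of 30% in everyone. Power is P(X ≥ 12 | 46 − k, 0.30), and expected observed ORR is 0.30 × (46 − k)/46.

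| k (assumed) | Expected ORR | Power | Size at ORR 15% |
|---|---|---|---|
| 0 | 30.0% | 0.767 | 0.035 |
| 1 | 29.3% | 0.738 | 0.030 |
| 2 | 28.7% | 0.706 | 0.026 |
| 5 | 26.7% | 0.599 | 0.015 |

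As a population share f, with p = 0.30 × (1 − f), power is 0.753 at 1% and 0.739 at 2%, a loss of 1.4 and 2.8 points. Because CR, VGPR, nCR and perhaps FLC-based PR remain open, these are upper bounds on the loss. If half of the affected subjects' responses still counted, power would be 0.737 for k = 2 and 0.689 for k = 5.

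**The case against.** **The literal reading proves too much.** A rule that also bars SD and PD looks like wording carried over from a source, not one meant to turn PRs into non-responses. That is plausible, and investigators may well have ignored it. But it shows that the footnote cannot be followed as written. It does not show which threshold was used.

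**The effect is hypothetical.** This stands in part. The documents give no affected share and do not show that any PR was withheld. Phase 2 was at the sponsor's discretion for each schedule, and the documents do not show that either schedule reached 46. Appendix N reports the primary analysis complete, so planning power can no longer be protected. The power figures therefore serve only to show sensitivity.

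**Stronger readings that a reader might infer.** One is that FLC-only subjects have no PR rule. The PR row gives them one, and as the more specific text it would probably be given effect. Another is that the sample size is wrong. It is not, since the stated design reproduces. A third is that 1.0 g/dL is simply a mistake for 0.5 g/dL. The documents do not show whether the higher figure is deliberate.

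**Conclusion.** The contradiction is real and sits in the definition of the primary endpoint. Eligible subjects with serum M-protein of 0.5 to below 1.0 g/dL and urine below 200 mg/24 h cannot be scored PR on M-protein as the protocol is written, and they remain in the ORR denominator. If footnote d was applied, the bias is downward and conservative: both power and type I error fall. The size depends on a share that must be assumed. It is about 1 to 3 points of power at a 1–2% share, and at most the loss to 60% if 5 of 46 were affected. It cannot be concluded from the documents that the reported ORR is in fact biased. The wording in Protocol Section 8 on subjects unevaluable for response rate is a separate issue.

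**What to change.** Reconcile footnote d, the PR row, footnote a, the PD row and inclusion criterion 1 to one definition of measurable disease. Aligning to criterion 1, including its FLC route, would make every eligible subject scorable. If 1.0 g/dL was intended, the protocol should say so and state how subjects below it are scored.

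The primary analysis is reported complete, so do not add a retrospective scoring rule to the SAP. SAP 1 already directs changes made after finalisation to the report. In the report or an addendum:

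- state which rule was applied;
- list responders by baseline disease type: serum ≥ 1.0 g/dL; serum 0.5 to < 1.0 g/dL, split by urine below or at least 200 mg/24 h; urine only; FLC only;
- give ORR under both rules by rescoring the affected subjects, labelled post hoc.

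**Cost.** No new patients or samples are needed: Appendix E schedules SPEP and UPEP and requires SFLC for all subjects. Rescoring investigator-assessed responses is modest work. Two drawbacks remain. A PR at low M-protein rests on a small absolute change: 50% of 0.5 is 0.25 g/dL, against 0.5 g/dL from a baseline of 1.0. Under criterion 1, subjects with serum 0.5 to < 1.0 g/dL and urine ≥ 200 mg/24 h would come under footnote a's both-tests rule, so some PRs could be lost. Reporting both rules makes this visible.
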